5. TREATMENT PLAN

This is a multicenter open-label phase 2 trial evaluating atezolizumab in adult subjects ≥ 18 years of age and in pediatric/adolescent subjects ≥ 2 years of age with advanced CCS or CS. Patients will be divided into cohorts based on histology upon enrollment. There will be three cohorts: histologically confirmed CCS (or EWSR1 translocation), conventional CS (grade 2 or 3), and dedifferentiated CS.

Patient evaluations will be performed throughout the study as described below. Baseline history, physical examination, laboratory evaluations, urinalysis, and EKG are to be conducted within 8 days prior to the start of protocol therapy. If protocol therapy is started within 8 days of these eligibility screening evaluations (see Section [3.3](#)), values from the screening evaluations may be used as baseline measurements; if >8 days have passed since the screening evaluations, the medical history, physical examination, laboratory evaluations, urinalysis, and EKG must be repeated prior to starting protocol therapy. Baseline imaging scans and ECHO must be done within 28 days prior to the start of protocol therapy.

History and physical examination will be done within 8 days of Day 1 of all cycles. Labs (serum chemistries and CBC with differential) will be performed at baseline as described above, on Cycle 1 Day 15 [± 1 day], and then up to 3 days before the start of each subsequent cycle (LDH and protein do not need to be checked again after baseline). TSH will be checked at baseline (within 8 days of Cycle 1 Day 1) and then up to 3 days before the start of each subsequent cycle. EKG will be repeated as clinically indicated after the baseline measurement described above.

Patients will have a CT scan at baseline (within 28 days prior to start of protocol therapy). Patients will undergo a CT scan and be re-evaluated for response at the end of Cycle 3 and every two cycles thereafter (every 3 cycles for patients on study for >1 year; every 4 cycles for patients on study for >2 years). Given the concern of pseudoprogression ("tumor flare"), patients that are clinically well may continue on therapy following RECIST progression if they meet the criteria outlined in Section 11.4.

Research biopsies (mandatory for adult patients at all sites) and blood samples for PD studies (mandatory for patients ≥ 12 years of age) will be collected as described in Section [9.2](#) and Section [9.3](#).

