a: Atezolizumab dose as assigned; adults ≥ 18 years at 1200 mg IV and in pediatric/adolescents ≥ 2 years at 15 mg/kg (max single dose=1200 mg); drug will be administered once on Day 1 only of each cycle. Each cycle is 21 days (± 3 days). Start of new cycle may be delayed up to 2 weeks to accommodate scheduling conflicts.

b: History and physical at baseline and up to 8 days before the start of each subsequent cycle.

c: CBC w/diff, plts, and serum chemistry (ACTH, albumin, alkaline phosphatase, AM cortisol, amylase, bicarbonate, total bilirubin, BUN, calcium, chloride, creatinine, glucose, LDH, lipase, phosphorus, potassium, pregnancy test per institutional standard at each participating site, total protein, SGOT [AST], SGPT [ALT], sodium, free T4) at baseline and then up to 3 days before the start of each subsequent cycle. After baseline, amylase, LDH, lipase, protein, and free T4 do not need to be checked.

d: TSH levels at baseline and then up to 3 days before the start of each subsequent cycle.

e: Baseline and as indicated.

f: CT scan or other imaging test at baseline, at the end of Cycle 3, and every two cycles thereafter (every 3 cycles for patients on study for >1 year; every 4 cycles for patients on study for >2 years).

g: Serum or urine pregnancy test (women of childbearing potential) within 8 days prior to enrollment. If

clinically indicated, serum or urine pregnancy test is required for women of childbearing potential ≤ 8 days before the start of each treatment cycle [per institutional standard at each participating site]; outside lab results are acceptable.

- h: Adult patients (≥ 18 years of age; mandatory at all sites), at baseline and prior to C3D1 (± 3 days) or sooner if there is clinical evidence that the patient is responding to drug, as described in Section [9.2.1](#).
- i: One optional tumor biopsy may be collected following progression or a 10-19% increase in tumor volume at restaging, as described in Section [9.2.1](#).
- j: Eligibility screening results may be used for these baseline measurements if conducted within 8 days (for medical history, physical exam, CBC, serum chemistry, TSH, and EKG) or 28 days (for ECHO) prior to the start of protocol therapy. See Sections [3.3](#) and [5](#).
- k: **At NCI only:** blood for ImmunoPD (mandatory from patients ≥ 12 years of age) on C1D1, C1D15 (optional), day one of each cycle, and at restaging follow up or progression as described in Section [9.3](#).

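### After the first dose the pregnancy-test schedule is internally inconsistent, and a compliant site may re-dose a woman of childbearing potential without a test

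*Combined protocol and SAP*

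**What the plan says.** Before treatment the rule is firm. Section 3.3.4 requires a serum or urine test for women of childbearing potential within 8 days of both enrollment and the start of therapy.

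After that, three entries in the Study Calendar (Section 10) bear on the test:

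- **B-HCG row.** It carries an unadorned X at Cycle 2, Cycle 3 and Cycles 4+. The row label refers to footnote g.
- **Footnote c.** The chemistry panel includes "pregnancy test per institutional standard at each participating site, total protein" and other analytes. The panel is due "at baseline and then up to 3 days before the start of each subsequent cycle". The footnote then names what lapses: "After baseline, amylase, LDH, lipase, protein, and free T4 do not need to be checked". The pregnancy test is not on that list.
- **Footnote g.** The enrollment test is unconditional. For treatment cycles the sentence opens with an if: "clinically indicated, serum or urine pregnancy test is required for women of childbearing potential", no more than 8 "days before the start of each treatment cycle [per institutional standard at each participating site]; outside lab results are acceptable".

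Section 5 names chemistries, CBC and TSH before each cycle but no pregnancy test, so it does not settle the question.

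**The concern.** A coordinator reading the row would schedule a test at every cycle. One reading footnote c would probably do the same, within 3 days and subject to the site's standard. One reading footnote g would test only when something prompts it, within 8 days. In a multicenter trial these readings can lead to different practice at different sites, all of it compliant.

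Section 3.1.13 states a fetal risk that extends to embryo-lethality, and Section 5.3 makes pregnancy a reason to stop treatment, so finding a pregnancy changes dosing. The issue is participant safety and consistency of conduct. It has no bearing on response rate, the two-stage rule or its operating characteristics.

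**Working it through.** No figure in the plan needs reproducing. The check sets the instructions side by side and then counts the doses concerned.

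**1. The instructions compared (doses after the first)**

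| Source | Condition | Window before cycle | Site discretion stated |
|---|---|---|---|
| B-HCG row | none shown | none shown | none shown |
| Footnote c | none beyond site standard | 0 to 3 days | yes |
| Footnote g | only if clinically indicated | 0 to 8 days | yes |
| Section 3.3.4 | not applicable (enrollment and start of therapy only) | – | – |
| Section 5 | pregnancy test not named | – | – |

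Footnotes c and g differ in two respects: the clinical-indication condition and the window. A test done 4 to 8 days before a cycle satisfies g but not c. A test within 3 days satisfies both.

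**2. Does the calendar's own convention resolve the row?**

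Optional cells elsewhere are flagged in the cell itself: the Cycle 1 Week 3 PD blood draw carries superscript k, and the off-treatment biopsy carries superscript i. EKG and echocardiogram, which footnote e describes as done at baseline and as indicated, have no X at Cycles 2, 3 or 4+. The later B-HCG cells are marked and carry no flag of their own. By that convention the row reads as scheduled, although its label points to a conditional footnote.

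**3. Doses per woman not firmly covered by footnote g**

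Inputs: "drug will be administered once on Day 1 only of each cycle" (footnote a); 21-day cycles; "Patients will undergo a CT scan and be re-evaluated for response at the end of Cycle 3" (Section 5).

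- By the first restaging: 3 infusions − 1 = **2** after the first.
- First year, no delay and no early stop: (365 − 1) / 21 = 17.3, so **17** after the first. The 17th falls on day 1 + 17 × 21 = 358; the next would be day 379, outside the year.
- For scale, Section 2.3.4.3 reports a median of 5.0 cycles in the phase 1a study of this drug: 5 − 1 = 4 later doses. That is another population and is only indicative here.

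**4. How many women**

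The Section 13.2 table plans 27 + 4 = 31 females out of 68. That is only an upper bound on the planned number: the documents do not state how many are of childbearing potential, what each site's standard is, or any pregnancy rate. No trial total can be derived.

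**The case against.** The strongest reply is that there is no real conflict. Footnote g is attached to the B-HCG row, so it defines what the row's marks mean. Both footnotes defer to institutional standard, so footnote c sets no firm rule for g to contradict. On this view indication-based testing is a deliberate policy.

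The reply adds that the protections work as a chain. Contraception is required (3.1.13). Women are told to contact the investigator at once if they suspect pregnancy (5.3). At the clinic, "History and physical examination will be done within 8 days of Day 1 of all cycles". Once there is an indication, footnote g makes the test mandatory. Pregnancy then ends treatment and is reported and followed (5.3, 7.5).

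Much of this stands. A reader might infer that the row and footnote g flatly contradict each other; the documents do not support that, because g can fairly be read as qualifying its own row. A reader might infer that footnote c mandates a test at every cycle; its site-standard wording stops short of that. A reader might also infer that nothing protects women after the first dose; the chain above shows otherwise.

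Two things do not go away. Footnote c has no clinical-indication condition and uses a different window, so c and g still give different instructions and neither is named as governing. And each step that leads to an indicated test needs somebody to suspect pregnancy first. An unrecognized pregnancy, with no missed period reported and nothing found at the visit, meets no scheduled test under footnote g. Under footnote c the same can happen where the site's standard does not call for one.

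**Conclusion.** The inconsistency is real and modest. After the first dose the row, footnote c and footnote g do not state one rule, and a site that follows footnote g can give atezolizumab to a woman of childbearing potential without a test. Per woman, this concerns 2 doses by the first restaging and at most 17 in the first year; the 17 assumes no delay, progression or withdrawal and is a ceiling.

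A reader might go further and infer that the first dose is unprotected, or that pregnancies will be missed at some rate. Section 3.3.4 rules out the first, and the documents give no basis for the second. The point should be corrected because the stated fetal risk is serious and the remedy is cheap. It does not call the trial's design or analysis into question.

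**What to change.** Adopt one rule and state it once.

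- **Footnote g:** delete the clinical-indication condition and the bracketed site-standard clause. Suggested text: *Serum or urine pregnancy test for all women of childbearing potential within 8 days of enrollment and of the start of therapy (Section 3.3.4), and within 8 days before every later cycle. Choice of serum or urine follows institutional standard; results from outside laboratories may be used.*
- **Footnote c:** replace the pregnancy-test entry with *pregnancy test: see footnote g*.

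Keeping 8 days is enough to remove the window difference. A 3-day window is an option, since CBC, chemistry and TSH already use it. The B-HCG row needs no change.

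The cost is two footnote edits and one inexpensive test per woman per cycle, which can be done with the laboratory work already drawn before each cycle. Sites lose discretion over whether to test but keep it over how. There is no effect on the primary endpoint, the sample size or the analysis.

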11. MEASUREMENT OF EFFECT

11.1 Antitumor Effect – Solid Tumors

Patients should be re-evaluated for response at the end of Cycle 3 (before Cycle 4), and at the end of every two cycles thereafter (before every even-numbered cycle). Restaging scans may be performed less frequently for patients on study for more than 1 year (every three cycles for patients on study for more than 1 year; every four cycles for patients on study more than 2 years). Confirmatory scans should also be obtained ≥ 4 weeks following initial documentation of objective response.

Response and progression will be evaluated in this study using the international criteria proposed by the revised Response Evaluation Criteria in Solid Tumors (RECIST) guideline (version 1.1) [59]. Changes in the largest diameter (unidimensional measurement) of the tumor lesions and the shortest diameter in the case of malignant lymph nodes are used in the RECIST criteria.

Patients that are clinically well may continue on therapy following RECIST progression with new lesions or increase in target lesions, provided the criteria in Section [11.4](#) are met.

Response will also be explored using iRECIST (see Section [11.3](#)). Increasing clinical experience indicates that traditional response criteria such as RECIST may not be sufficient to fully characterize activity in the new era of target therapies and/or biologics. In studies with therapeutic antibodies, complete response, partial response, or stable disease has been shown to occur after an increase in tumor burden, characterized by progressive disease by traditional response criteria. Therefore, conventional response criteria may not adequately assess the activity of immunotherapeutic agents because progressive disease (by initial radiographic evaluation) does not necessarily reflect therapeutic failure. Long-term effect on the target disease must also be captured. The iRECIST criteria, by incorporating specific response patterns

that have been observed with immunotherapeutic agents, have been developed to address these issues and provide standardized response criteria for use with immunotherapy [60].

11.2 RECIST Response Assessment

11.2.1 Definitions

Evaluable for Toxicity. All patients will be evaluable for toxicity from the time of their first treatment with atezolizumab.

Evaluable for Objective Response Rate. Only those patients who have measurable disease present at baseline and have received at least one dose of therapy will be considered evaluable for the primary endpoint of objective response rate. These patients will have their response classified according to the definitions stated below. (Note: Patients who exhibit objective disease progression prior to the end of Cycle 1 will also be considered evaluable.)

Evaluable Non-Target Disease Response. Patients who have lesions present at baseline that are evaluable but do not meet the definitions of measurable disease, have received at least one cycle of therapy, and have had their disease re-evaluated will be considered evaluable for non-target disease. The response assessment is based on the presence, absence, or unequivocal progression of the lesions.

11.2.2 Disease Parameters

Measurable Disease. Measurable lesions are defined as those that can be accurately measured in at least one dimension (longest diameter to be recorded) as ≥ 20 mm (≥ 2 cm) by chest x-ray or as ≥ 10 mm (≥ 1 cm) with CT scan, MRI, or calipers by clinical exam. All tumor measurements must be recorded in millimeters (or decimal fractions of centimeters).

Malignant Lymph Nodes. To be considered pathologically enlarged and measurable, a lymph node must be ≥ 15 mm (≥ 1.5 cm) in short axis when assessed by CT scan (CT scan slice thickness recommended to be no greater than 5 mm [0.5 cm]). At baseline and in follow-up, only the short axis will be measured and followed.

Non-Measurable Disease. All other lesions (or sites of disease), including small lesions (longest diameter < 10 mm [< 1 cm] or pathological lymph nodes with ≥ 10 to < 15 mm [≥ 1 to < 1.5 cm] short axis), are considered non-measurable disease. Bone lesions, leptomeningeal disease, ascites, pleural/pericardial effusions, lymphangitis cutis/pulmonitis, inflammatory breast disease, and abdominal masses (not followed by CT or MRI), are considered as non-measurable.

Note: Cystic lesions that meet the criteria for radiographically defined simple cysts should not be considered as malignant lesions (neither measurable nor non-measurable) since they are, by definition, simple cysts.

‘Cystic lesions’ thought to represent cystic metastases can be considered as measurable lesions, if they meet the definition of measurability described above. However, if non-cystic lesions are

present in the same patient, these are preferred for selection as target lesions.

Target Lesions. All measurable lesions up to a maximum of 2 lesions per organ and 5 lesions in total, representative of all involved organs, should be identified as **target lesions** and recorded and measured at baseline. Target lesions should be selected on the basis of their size (lesions with the longest diameter), be representative of all involved organs, but in addition should be those that lend themselves to reproducible repeated measurements. It may be the case that, on occasion, the largest lesion does not lend itself to reproducible measurement in which circumstance the next largest lesion which can be measured reproducibly should be selected. A sum of the diameters (longest for non-nodal lesions, short axis for nodal lesions) for all target lesions will be calculated and reported as the baseline sum diameters. If lymph nodes are to be included in the sum, then only the short axis is added into the sum. The baseline sum diameters will be used as reference to further characterize any objective tumor regression in the measurable dimension of the disease.

Non-Target Lesions. All other lesions (or sites of disease) including any measurable lesions over and above the 5 target lesions should be identified as **non-target lesions** and should also be recorded at baseline. Measurements of these lesions are not required, but the presence, absence, or in rare cases unequivocal progression of each should be noted throughout follow-up.

11.2.3 Methods for Evaluation of Measurable Disease

All measurements should be taken and recorded in metric notation using a ruler or calipers. All baseline evaluations should be performed as closely as possible to the beginning of treatment and never more than 4 weeks before the beginning of the treatment.

The same method of assessment and the same technique should be used to characterize each identified and reported lesion at baseline and during follow-up. Imaging-based evaluation is preferred to evaluation by clinical examination unless the lesion(s) being followed cannot be imaged but are assessable by clinical exam.

Clinical Lesions. Clinical lesions will only be considered measurable when they are superficial (*e.g.*, skin nodules and palpable lymph nodes) and ≥ 10 mm (≥ 1 cm) diameter as assessed using calipers (*e.g.*, skin nodules). In the case of skin lesions, documentation by color photography, including a ruler to estimate the size of the lesion, is recommended.

Chest X-Ray. Lesions on chest x-ray are acceptable as measurable lesions when they are clearly defined and surrounded by aerated lung. However, CT is preferable.

Conventional CT and MRI. This guideline has defined measurability of lesions on CT scan based on the assumption that CT slice thickness is 5 mm (0.5 cm) or less. If CT scans have slice thickness greater than 5 mm (0.5 cm), the minimum size for a measurable lesion should be twice the slice thickness. MRI is also acceptable in certain situations (*e.g.* for body scans).

Use of MRI remains a complex issue. MRI has excellent contrast, spatial, and temporal resolution; however, there are many image acquisition variables involved in MRI, which greatly

impact image quality, lesion conspicuity, and measurement. Furthermore, the availability of MRI is variable globally. As with CT, if an MRI is performed, the technical specifications of the scanning sequences used should be optimized for the evaluation of the type and site of disease. Furthermore, as with CT, the modality used at follow-up should be the same as was used at baseline and the lesions should be measured/assessed on the same pulse sequence. It is beyond the scope of the RECIST guidelines to prescribe specific MRI pulse sequence parameters for all scanners, body parts, and diseases. Ideally, the same type of scanner should be used and the image acquisition protocol should be followed as closely as possible to prior scans. Body scans should be performed with breath-hold scanning techniques, if possible.

PET-CT. At present, the low dose or attenuation correction CT portion of a combined PET-CT is not always of optimal diagnostic CT quality for use with RECIST measurements. However, if the site can document that the CT performed as part of a PET-CT is of identical diagnostic quality to a diagnostic CT (with IV and oral contrast), then the CT portion of the PET-CT can be used for RECIST measurements and can be used interchangeably with conventional CT in accurately measuring cancer lesions over time. Note, however, that the PET portion of the CT introduces additional data which may bias an investigator if it is not routinely or serially performed.

Ultrasound. Ultrasound is not useful in assessment of lesion size and should not be used as a method of measurement. Ultrasound examinations cannot be reproduced in their entirety for independent review at a later date and, because they are operator dependent, it cannot be guaranteed that the same technique and measurements will be taken from one assessment to the next. If new lesions are identified by ultrasound in the course of the study, confirmation by CT or MRI is advised. If there is concern about radiation exposure at CT, MRI may be used instead of CT in selected instances.

Endoscopy, Laparoscopy. The utilization of these techniques for objective tumor evaluation is not advised. However, such techniques may be useful to confirm complete pathological response when biopsies are obtained or to determine relapse in trials where recurrence following complete response (CR) or surgical resection is an endpoint.

Tumor Markers. Tumor markers alone cannot be used to assess response. If markers are initially above the upper normal limit, they must normalize for a patient to be considered in complete clinical response. Specific guidelines for both CA-125 response (in recurrent ovarian cancer) and PSA response (in recurrent prostate cancer) have been published [61-63]. In addition, the Gynecologic Cancer Intergroup has developed CA-125 progression criteria which are to be integrated with objective tumor assessment for use in first-line trials in ovarian cancer [64].

Cytology, Histology. These techniques can be used to differentiate between partial responses (PR) and complete responses (CR) in rare cases (*e.g.*, residual lesions in tumor types, such as germ cell tumors, where known residual benign tumors can remain).

The cytological confirmation of the neoplastic origin of any effusion that appears or worsens during treatment when the measurable tumor has met criteria for response or stable disease is

mandatory to differentiate between response or stable disease (an effusion may be a side effect of the treatment) and progressive disease.

FDG-PET. While FDG-PET response assessments need additional study, it is sometimes reasonable to incorporate the use of FDG-PET scanning to complement CT scanning in assessment of progression (particularly possible 'new' disease). New lesions on the basis of FDG-PET imaging can be identified according to the following algorithm:

- a. Negative FDG-PET at baseline, with a positive FDG-PET at follow-up is a sign of PD based on a new lesion.
- b. No FDG-PET at baseline and a positive FDG-PET at follow-up: If the positive FDG-PET at follow-up corresponds to a new site of disease confirmed by CT, this is PD. If the positive FDG-PET at follow-up is not confirmed as a new site of disease on CT, additional follow-up CT scans are needed to determine if there is truly progression occurring at that site (if so, the date of PD will be the date of the initial abnormal FDG-PET scan). If the positive FDG-PET at follow-up corresponds to a pre-existing site of disease on CT that is not progressing on the basis of the anatomic images, this is not PD.
- c. FDG-PET may be used to upgrade a response to a CR in a manner similar to a biopsy in cases where a residual radiographic abnormality is thought to represent fibrosis or scarring. The use of FDG-PET in this circumstance should be prospectively described in the protocol and supported by disease-specific medical literature for the indication. However, it must be acknowledged that both approaches may lead to false positive CR due to limitations of FDG-PET and biopsy resolution/sensitivity.

Note: A 'positive' FDG-PET scan lesion means one which is FDG avid with an uptake greater than twice that of the surrounding tissue on the attenuation corrected image.

